9.4.7 INTERIM ANALYSES

While recruitment is ongoing, interim results will be supplied, in strict confidence, to the ISM as frequently as requested. All individuals involved in the interim analyses, including the biostatistician, will be blinded to intervention assignment.

Interim analysis of the study will be conducted based on the alpha spending rule .²⁶ The proportion of the observed sample size (number of patients observed divided by the target sample size) will be considered as the information statistics. The p-value will be adjusted to maintain the overall study power of 0.05, two-sided.

The ISM will inform the PI of the results only if the test statistics exceeds the adjusted p-value in the primary efficacy or safety outcome and if, in the opinion of the ISM, the study should be considered for early termination. The study would not be terminated early if the difference is found only in a secondary outcome of efficacy, the p-value is smaller but close to the adjusted p-value, or when the variance is small. The decision to terminate the study early would be made by the ISM with consultation of a non-treating physician as needed.

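### Section 9.4.7 bars early termination when an undefined variance is small, a condition that adds no needed error control and can block a valid boundary crossing

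*Combined protocol and SAP*

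**What the plan says.** Section 9.4.7 sets up the interim looks: "Interim analysis of the study will be conducted based on the alpha spending rule". Information is measured as "number of patients observed divided by the target sample size", so variance plays no part in the spending scheme. The overall two-sided level is 0.05, although the text calls it power: "The p-value will be adjusted to maintain the overall study power of 0.05, two-sided". The spending function and the number and timing of looks are not given.

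The Independent Safety Monitor (ISM) informs the principal investigator "only if the test statistics exceeds the adjusted p-value in the primary efficacy or safety outcome", and only if the ISM also thinks that stopping should be considered. The next sentence restricts stopping. It begins "The study would not be terminated early if the difference is found only in a secondary outcome of efficacy" and continues with two further conditions: "the p-value is smaller but close to the adjusted p-value, or when the variance is small". The first condition is confined to efficacy; the variance condition, "or when the variance is small", is not. Neither *variance* nor *small* is defined, no reason is given, and no other section qualifies the clause. The section closes by assigning the decision: "The decision to terminate the study early would be made by the ISM", with a non-treating physician consulted as needed.

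Section 10.1.2 lists grounds for ending the study, among them unacceptable risk and demonstrated efficacy. None carries a variance condition.

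**The concern.** An alpha-spending boundary is a limit on a p-value. The p-value for a difference in mean days is computed from the difference divided by its estimated standard error, so the observed variance is already in it. Adding small variance as a reason not to stop counts the variance a second time, and in the wrong direction: with the difference held fixed, lower variance means stronger evidence.

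Two things are at stake. First, a look that crosses the boundary validly may not be acted on, although the alpha for that look has been spent and the final threshold is stricter as a result. Second, because the condition has no threshold, the ISM cannot apply it reproducibly, and a threshold could be chosen after the interim data are seen. The clause also reaches a crossing on the safety outcome, where it does not fit with section 10.1.2.

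**Working it through.** **Inputs from the documents.** Three equal arms, f = 0.28, 80% power, two-sided alpha 0.05, 126 participants before inflation and 147 after (section 9.2); a GLM on days to RTS (section 9.4.2); alpha spending on the fraction of participants observed (section 9.4.7).

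**Assumptions.** The documents give no standard deviation, no effect in days, no look times, no spending function and no cut-off for *small*. The figures used for these below are illustrations. The test is taken as the normal-theory F test.

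**1. The plan's own figure.** One-way F test, 2 and N − 3 degrees of freedom, noncentrality N × f². At N = 126: 126 × 0.28² = 9.88, power 0.8002. At N = 123 power is 0.790. The stated 126 is reproduced, which supports using the F test here.

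**2. The variance is already in the p-value.** Take two arms of 25 and a fixed difference of 7 days, with t = 7 / (SD × √(2/25)) on 48 degrees of freedom.

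| SD (days) | t | two-sided p |
|---|---|---|
| 6 | 4.12 | 0.00015 |
| 8 | 3.09 | 0.0033 |
| 10 | 2.47 | 0.017 |
| 14 | 1.77 | 0.083 |

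For the same difference, the smaller variance is what produces the crossing.

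**3. Error control without the clause.** Simulated three-arm looks with no true effect cross p < 0.003 at a rate of 0.0029 to 0.0032 for N between 36 and 108. The nominal level is held with no variance condition.

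**4. How many crossings the clause would veto.** Simulated look at N = 72 (24 per arm, about half of 147), one arm differing so that f = 0.28. *Small* is taken as the pooled variance falling in the stated lower part of its sampling distribution.

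| Meaning of *small* | vetoed at p < 0.003 | vetoed at p < 0.03 |
|---|---|---|
| below the median | 67–68% | 58% |
| lowest quartile | 40% | 32% |
| lowest decile | 19% | 14% |

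Each share exceeds the unconditional 50%, 25% or 10%, because crossings tend to occur when the observed variance is low.

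**5. Power lost if every interim crossing were vetoed.** Sequential 2-df statistic, noncentrality 9.634 (which gives 80.0% power for a fixed 2-df chi-square test at 5%), Lan-DeMets spending, one look at half information or four equally spaced looks before the final analysis.

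| Design | crossings honoured | all interim crossings vetoed | loss due to veto |
|---|---|---|---|
| one O'Brien-Fleming-type look | 79.6% | 79.4% | 0.2 points |
| one Pocock-type look | 74.9% | 72.4% | 2.5 points |
| four Pocock-type looks | 71.1% | 65.7% | 5.4 points (up to 5.6 across runs) |

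The gap between 80.0% and the middle column is the cost of looking and remains if the clause is deleted. The last column is the most that the clause can cost, since it supposes a veto of every interim crossing.

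**The case against.** The strongest defence is that the clause is only a caution. It can make efficacy stopping more conservative but cannot inflate type I error, and it changes neither the final test nor the estimate. The ISM decides, judgement is already built in, and section 10.1.2 gives other grounds for stopping. All of this limits the harm. It does not rescue the wording, because the sentence is phrased as a prohibition and the ISM's discretion is stated separately, in the sentence before it.

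A second defence is that the clause may be meant to guard against a variance that is low by chance at an early look. It would have some such effect: at N = 63 with a median cut-off and a boundary of p < 0.00305, it vetoes 86% of crossings when there is no effect against 70% at f = 0.28. But the F reference distribution already allows for an uncertain variance. If a large-sample Wald test is used instead, control at small N is only approximate, and a minimum number of participants would address that directly. If the worry is a trivial difference, the quantity to limit is the difference in days.

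A reader might go further and infer three things that the documents do not support:

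- **That the clause blocks most correct stops.** This needs a generous threshold. Observed variance is below its true value in about 70% of crossings at p < 0.003 and 60% at p < 0.03 (N = 72), but it is also below its true value in about 52% of all such datasets. An event that happens about half the time is hardly *small*. With the lowest decile, most crossings survive.
- **That it takes power from 80% to about 72% or 66%.** Most of that drop is the cost of Pocock-type looks, as step 5 shows.
- **That the sponsor meant to penalise precision.** The text gives no motive, and the phrase may be a garbled version of a sensible caution.

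**Conclusion.** The point holds. The clause states a condition that runs against the logic of the test, has no link to the spending rule, and cannot be applied as written. It can block a valid crossing on the primary efficacy outcome. As worded it also covers the safety outcome, and sections 9.4.7 and 10.1.2 must be reconciled on that.

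The size is modest and conditional. At f = 0.28, N = 72 and p < 0.003, the share of crossings vetoed runs from about 19% (lowest decile) to about 67% (below the median). The upper limit on lost power is about 0.2, 2.5 or 5.6 points under the three assumed designs, in addition to valid early stops forgone. Type I error is not inflated. These figures rest on a normal-theory F test and on assumed look times, spending functions and cut-offs. The direction of the defect does not depend on those choices of look times, spending functions and cut-offs.

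**What to change.** Delete "or when the variance is small" from section 9.4.7 before any further interim look, and reconcile the remaining stopping text with the grounds in section 10.1.2, particularly for a safety crossing.

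Nothing more is required. If the sponsor did want protection against unreliable early estimates or trivial differences, it should say so directly and for efficacy looks only, as a minimum number of participants observed or a minimum difference in days, with values that the sponsor chooses and fixes before the next look.

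The cost is one sentence in an amendment. No participants, visits or procedures change.

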10 SUPPORTING DOCUMENTATION AND OPERATIONAL CONSIDERATIONS

10.1 REGULATORY, ETHICAL, AND STUDY OVERSIGHT CONSIDERATIONS

10.1.1 INFORMED CONSENT PROCESS

10.1.1.1 CONSENT/ASSENT AND OTHER INFORMATIONAL DOCUMENTS PROVIDED TO PARTICIPANTS

Consent forms describing in detail the study intervention, study procedures, and risks will be given to the participant and written documentation of informed consent will be completed either in written form in the participant's chart or directly into the electronic medical record. The following consent materials are submitted with this protocol:

- Informational Flyer this flyer describes the basics of the study and contact information
 of the PI. This flyer serves as a means of providing the potential participant and their
 parent general information to review prior to their first visit with the physical therapist.
 This flyer will be available in the office settings of the CHKD Primary Care Sports
 Medicine physician's offices and CHKD Orthopedic Surgeon's offices.
- Patient Informed Consent Form
- Assent Form

10.1.1.2 CONSENT PROCEDURES AND DOCUMENTATION

Patients seen by CHKD Primary Care Sports Medicine physicians or CHKD Orthopedic physicians with a diagnosis of apophysitis of the knee and referred to CHKD PT for PT treatment and iontophoresis treatment will be potential subjects for the study. The referring physician will provide written approval to the Treating Therapist that the patient may be considered for enrollment into this study. The referring physician may provide an IRB-approved Informational Flyer to the parent and child for their review prior to meeting with the Physical Therapist. The Principal Investigator's (PI) contact information will be provided on the Informational Flyer. Parents may choose to call the PI to discuss the study or request that the informational packet be emailed or mailed to them in advance of their IE Visit.

As standard of care, all patients referred for PT treatment and iontophoresis receive an IE in one of the CHKD PT clinics. After the Treating Therapist receives the referral and prior to the IE, the Treating Therapist will ensure the referring physician has provided written approval for the patient to be

considered for enrollment in the study. Once approval is secured, the Treating Therapist may contact the parent to discuss the study and answer any questions they may have. At the IE, the Treating Therapist will discuss the study with the patient and his/her parent/legally authorized representative (LAR) in detail and if interested in participating in the study, will provide them a copy of the IRB-approved informed consent and assent forms for review.

Patients will have the opportunity to carefully review the written consent form and ask questions prior to signing. The patients will have the option to sign Consent on the day of the IE or take more time to consider it and decide at the beginning of their next Standard PT Treatment visit.

Informed consent will only occur at the PT clinics and will be conducted by the Treating Therapists who have been CITI trained. The Informed consent process will be initiated prior to the individual's agreeing to participate in the study and will continue throughout the individual's study participation. No study-specific procedures will be conducted until the Consent and Assent Forms are signed and dated.

Participants will be informed that participation is voluntary and that they may withdraw from the study at any time, without prejudice. A copy of the informed consent document will be given to the participants for their records and the original scanned into the medical record and then stored in a locked office with the other essential documents of the study. The informed consent process will be conducted and documented in the source document. Participants who turn 18 years old or are emancipated during the course of the study will be re-consented.

The rights and welfare of the participants will be protected by emphasizing to them that the quality of their medical care will not be adversely affected if they decline to participate in this study.

10.1.2 STUDY DISCONTINUATION AND CLOSURE

This study may be temporarily suspended or prematurely terminated if there is sufficient reasonable cause. Written notification, documenting the reason for study suspension or termination, will be provided by the Principal Investigator to the Study Team, study participants, the EVMS IRB, and the CHKD HRC. If the study is prematurely terminated or suspended, the Principal Investigator (PI) will promptly inform study participants, the IRB, and will provide the reason(s) for the termination or suspension. Study participants will be contacted, as applicable, and be informed of changes to study visit schedule.

Circumstances that may warrant termination or suspension include, but are not limited to:

- Determination of unexpected, significant, or unacceptable risk to participants
- Demonstration of efficacy that would warrant stopping
- Insufficient compliance to protocol requirements
- Data that are not sufficiently complete and/or evaluable
- Determination that the primary endpoint has been met
- Determination of futility

Study may resume once concerns about safety, protocol compliance, and data quality are addressed, and satisfy the IRB.

Participant confidentiality and privacy is strictly held in trust by the participating investigators, and their staff. This confidentiality is extended to cover the clinical information relating to participants. Therefore, the study protocol, documentation, data, and all other information generated will be held in strict confidence. No information concerning the study or the data will be released to any unauthorized third party without prior written approval of the sponsor.

All research activities will be conducted in as private a setting as possible.

Authorized representatives of the sponsor, representatives of the Institutional Review Board (IRB), and regulatory agencies may inspect all documents and records required to be maintained by the investigator, including but not limited to, medical records (office, clinic, or hospital) and pharmacy records for the participants in this study. The clinical study site will permit access to such records.

The study participant's contact information will be securely stored at each clinical site for internal use during the study. At the end of the study, all records will continue to be kept in a secure location for as long a period as dictated by the regulations, the reviewing IRB, and institutional policies.

Study participant research data, which is for purposes of statistical analysis and scientific reporting, will be maintained in REDCap per institutional policy. This will not include the participant's contact or identifying information. Rather, individual participants and their research data will be identified by a unique study identification number. The study data entry and study management systems used by clinical sites will be secured and password protected.

10.1.5 SAFETY OVERSIGHT

Safety oversight will be under the direction of an ISM, an individual with the education, skills, and relevant expertise whose primary responsibility is to provide independent safety monitoring in a timely fashion. This is accomplished by review of adverse events with follow-up through resolution. The ISM, in consultation with a physician as needed, will evaluate individual and cumulative participant data when making recommendations regarding the continuation of the trial, modification to the trial, or termination of the trial in the event of unacceptable adverse events.

10.1.6 CLINICAL MONITORING

Internal site monitoring will be conducted to ensure that the rights and well-being of trial participants are protected, that the reported trial data are accurate, complete, and verifiable, and that the conduct of the trial is in compliance with the currently approved protocol/amendment(s), and with applicable regulatory requirements.

 On-site monitoring of this trial will be performed by qualified individuals within the CHKD Sports Medicine Team who have not participated in the enrollment or treatment of participants in this study. Monitoring will consist of 100% review of consent forms, inclusion/exclusion criteria, and RTS Checklist, and random review of remaining data points. A Monitoring Report will be provided to the Treating Therapist with a copy to the PI.

10.1.7 QUALITY ASSURANCE AND QUALITY CONTROL

All Treating Therapists will perform internal quality management of their own data collection, documentation and completion. The Treating Therapists will be responsible for correcting errors found by the Monitor.

Quality control (QC) procedures will be implemented beginning with the data entry system and data QC checks on the database will be generated. Any missing data or data anomalies will be communicated to the appropriate Treating Therapists for clarification/resolution.

The monitor will verify that the clinical trial is conducted and data are collected, documented (recorded), and reported in compliance with the protocol and applicable regulatory requirements.

The CHKD Investigational Pharmacist will monitor the Drug Accountability Logs for drug accountability. Any errors found will be corrected by the Treating Therapist.

All Treating Therapists will undergo site-specific protocol training as well training on obtaining and documenting Informed Consent and Good Documentation Principles. All Treating Therapists will

participate in training sessions conducted by the PI on adverse events (identifying, assessing, documenting, and reporting), the PT exercise protocol, Y balance testing, quad strength testing with hand-held dynamometer, iontophoresis patch preparation and application, administration of the patient-reported outcome measures (FACES Pain Scale and Godin Leisure-Time Activity Questionnaire), administration of the LEFS, and the RTS checklist. These sessions will include instructional handouts, demonstrations, and practice sessions to ensure good intra- and inter-examiner reliability.

The investigational site will provide direct access to all trial related sites, source data/documents, and reports for the purpose of monitoring and auditing by the sponsor, and inspection by local and regulatory authorities.

10.1.8 DATA HANDLING AND RECORD KEEPING

10.1.8.1 DATA COLLECTION AND MANAGEMENT RESPONSIBILITIES

Data collection is the responsibility of the Treating Therapists at the site under the supervision of the Principal Investigator. Treating Therapists will follow "Good Documentation Principles" when completing study related documentation. These principles will ensure data are: attributable, legible, contemporaneous, original, accurate, enduring, available and accessible, complete, consistent, credible, and corroborated.

Source data may take the form of hardcopy worksheets or electronic data, obtained from the participant's electronic medical record or paper chart, or through a REDCap survey. Per the CHKD Policy C1107 "Approval of Research", a copy of the signed Informed Consent will be scanned into the participant's electronic medical record. The treating physical therapist obtaining informed consent will place a consent note in the participant's paper chart as well as scan a copy into the electronic medical record.

Hardcopies of the study visit worksheets will be provided for use as source document worksheets for recording data for each participant enrolled in the study. The 30-Day Phone Follow Up Visits will be conducted by the Treating Therapist via a phone call to the participants and data obtained will be documented directly onto a visit worksheet. 90-Day Follow-Up Visits will be administered as REDCap surveys sent to the participant's email or cell phone with phone follow up as needed for new adverse events identified or new medications identified that may be associated with an adverse event.

All original source documents for a single participant will be collected from the treating PT clinic, following CHKD's Policy C3400.1 Transporting Protected Health Information, and transported and stored in the research office in a locked and secure cabinet.

All study-related clinical data will be entered into REDCap, a 21 CFR Part 11-compliant data capture system. The data system includes password protection and internal quality checks, such as automatic range checks, to identify data that appear inconsistent, incomplete, or inaccurate. Clinical data will be entered directly from the source documents.

10.1.8.2 STUDY RECORDS RETENTION

Study-related documents will be retained per the CHKD record retention policy.

10.1.9 PROTOCOL DEVIATIONS

A protocol deviation is any noncompliance with the clinical trial protocol or regulatory requirements. The noncompliance may be either on the part of the participant, the investigator, or the study site staff. As a result of deviations, corrective actions will be developed by the site and implemented promptly.

It is the responsibility of the Treating Therapists to use continuous vigilance to identify and report deviations within two (2) working days of identification of the protocol deviation to the Principal Investigator. All deviations will be documented in study source documents. Protocol deviations that result in a change to the risk/benefit ratio or affect the integrity of the study will be reported to the EVMS IRB per their SOPs.²⁵

10.1.10 PUBLICATION AND DATA SHARING POLICY

This study will comply with the Clinical Trials Registration and Results Information Submission rule. As such, this trial will be registered at ClinicalTrials.gov, and results information from this trial will be submitted to ClinicalTrials.gov. In addition, every attempt will be made to publish results in peer-reviewed journals.

Naming of authors and contributors to publications resulting from this research project will be determined in line with the International Committee of Medical Journal Editors' (ICMJE) recommendations.

